**FORM: Application for Human Research**

| NUMBER | FORM DATE | PAGE |
|--------|-----------|----------|
| F200 | 02/2014 | 40 of 44 |

1402 magnetic resonance spectroscopy imaging, analysis strategies, and statistical analysis of MRS and DTI
1403 data.

1404 Subjects may refuse to answer any questions that make them uncomfortable. In addition, subjects
1405 may terminate their participation in the study at any time. If significant psychopathology (e.g., threat of
1406 harm to self or others) is discovered at any time during or after a subject's visit, we will contact one of the
1407 psychiatrists on staff to determine the level of risk and establish a contract for safety. If the subject does
1408 not already have an established relationship with a psychiatrist, we will provide the appropriate referrals
1409 for psychiatric evaluation.

1410 Assessment of MRI scanning-related safety issues will occur at every scanning session by the
1411 study staff. Risks to subjects will be minimized by following standard MRI procedures. Individual scans
1412 will be aborted if any safety parameters are breached. If the safety issue involves the patient that cannot
1413 be eliminated within the time course of the study, their involvement in the study will be terminated. If the
1414 safety issue involves the scanner or the scanning environment, no further scans will be conducted from
1415 that point, until assurances are made that all safety parameters have returned to allowable limits.

1416 Female participants must have a negative pregnancy test before the MRI scan can be initiated. If
1417 the results of the pregnancy test are positive, one of the clinically trained study investigators will explain
1418 why the scan cannot be completed.

1419 No long-lasting physical or economic harm is anticipated during scanning. Every effort will be
1420 made to reassure the patient and minimize any such discomforts while scanning. Subjects will be offered
1421 and required to wear earplugs and/or earphones to minimize the scanner noise. Subjects will be able to
1422 converse with a staff member via a microphone and speaker system at all times during the scanning
1423 session. Subjects will be provided with an emergency button to indicate an immediate concern. Subjects
1424 may ask to have a scan stopped and discontinue participation in the study at any time.

1425 In case of an adverse event, the principal investigator will evaluate and report such events to the
1426 UA HSPP per UA HSPP guidelines as well as report to HRPO per federal guidelines.

1427 The diagnostic assessment, MRI, and heart rate measures may reveal previously unidentified
1428 psychiatric disorders and/or brain or heart abnormalities the subject didn't know they had. If any
1429 abnormalities are identified, they will be provided with information about the finding and encouraged to
1430 follow up with their primary care physician. Subjects will be made aware that we are not providing
1431 psychiatric, neuroradiological, or other clinical services; only that we will let them know in the event that
1432 anything abnormal is noticed by the study team. We are unable to assume responsibility or offer
1433 compensation for related medical costs that they make as a result of being informed of an abnormal
1434 finding.

1435 There may be instances in which an abnormality exists but is not identified in our analyses. Our team
1436 is not trained in clinically diagnosing issues pertaining to abnormalities found in the collected data.
1437 Further, our data analyses are not intended to treat, diagnose, or replace the expertise of a medical doctor
1438 or a medical diagnosis. Thus, subjects will be aware that they should not rely on our analyses to reveal
1439 abnormalities in their data, and our lab claims no responsibility for abnormalities that go undetected
1440 during participation in any research related activities.

1441
1442

**FORM: Application for Human Research**

| NUMBER | FORM DATE | PAGE |
|--------|-----------|----------|
| F200 | 02/2014 | 41 of 44 |

1443 15) Withdrawal of subjects

1444 If any disqualifying condition is discovered during the study or if it becomes evident that the
1445 participant is unable or unwilling to comply with study procedures, research study staff may withdraw
1446 that individual from the study.

1447 Subjects can voluntarily withdraw from the study at any time by speaking with the PI or study
1448 team. The study will then ensure the subject withdraws from the study safely and will provide any
1449 necessary follow-up care.

1450 In order to protect subjects, study resources and the integrity of study data, the Principal
1451 Investigator reserves the right to remove any subject at his discretion from the study. This will be
1452 communicated to prospective subjects during the consent process.

1453 If a subject chooses to withdraw from the study or his/her participation is ended prematurely, any
1454 information collected up to that point will be kept.

1455

1456 16) Sharing of results with subjects

1457 Subjects will be informed of any new information that pertains to their rights or safety
1458 immediately.

1459 Subjects have the right to see and get a copy of their health information that is used or shared for
1460 treatment or for payment. To ask for this information, subjects will contact the person in charge of this
1461 research study. Subjects may only get such information after the research is finished.

SECTION 4: LIST OF ATTACHMENTS FOR THIS SUBMISSION

| Document Name | Version Date |
|-----------------------------------|--------------|
| 1. F107 | 1. 06/10/14 |
| 2. Informed Consent Form | 2. 07/14/14 |
| 3. UAMC SRA Approval Letter | 3. 06/05/14 |
| 4. Grant Award/Notice of Funding | 4. 04/25/14 |
| 5. PI CV | 5. N/A |
| 6. goLITE Blu Pamphlet | 6. 2013 |
| 7. Edinburgh Handedness Inventory | 7. N/A |
| 8. PHQ-9 | 8. 1999 |
| 9. CAPS-5 | 9. N/A |
| 10. BDI -II | 10. N/A |
| 11. BAI | 11. N/A |
| 12. STAI | 12. N/A |
| 13. CD-RISC | 13. 09/21/11 |
| 14. PSQI | 14. 1989 |
| 15. ESS | 15. N/A |
| 16. DDNSI | 16. Unk |
| 17. SSS | 17. N/A |

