- All participants will be adults (age 18 to 50), thus issues regarding assent from minors are not relevant.

7) Procedures involved in the Human Research

General Procedure: Over a 4-year period, 108 participants between the ages of 18 and 50 will be recruited to participate (to reach a final n of 90 subjects, assuming 20% attrition). Participants will comprise active duty, Reserve, National Guard, or recently discharged combat-exposed military personnel or DoD contractors from Operation Enduring Freedom/Operation Iraqi Freedom (OEF/OIF) meeting DSM-V diagnostic criteria for PTSD, in addition to some non-military individuals who meet the DSM-V diagnostic criteria for PTSD. Combat-exposed individuals within 10 years of return from OIF/OEF will be eligible. An age range of 18-50 years has been selected to minimize possible developmental and degenerative effects that could be expected in younger and older subjects and to encompass the age range of the majority of military personnel.

FORM: Application for Human Research
NUMBER
FORM DATE
PAGE

F200

02/2014

23 of 44

724 Prior to data analysis, subjects who consent will have a follow-up phone call where they will be
 725 administered the PCL-5, PHQ-9, and be asked about general sleep problems using the ESS and ISI.
 726

727 The procedures will essentially be identical to those used successfully in our pilot study of patients
 728 with mTBI. Participants will attend three laboratory sessions (see Figure 10 below). Visit 1 involves
 729 informed consent, demographic data collection, and basic psychiatric assessment. Participants will be
 730 provided with a wrist actigraph sleep monitor. After a week of at home monitoring, each participant will
 731 return for Visit 2, which is involves comprehensive neurocognitive assessment, neuroimaging, fear
 732 conditioning testing, objective sleepiness monitoring and heart rate monitoring. Then participants will be
 733 randomly assigned to one of two light therapy conditions (n = 45 per group) differing only in the
 734 wavelength emitted by each light therapy device. Participants will be randomly assigned to either the BL
 735 condition or the PL condition, using computerized permuted block randomization to match groups by
 736 gender. Participants assigned to the active treatment condition will undergo 6-weeks of at-home treatment
 737 with a light device fitted with blue light (BL) diodes, while those assigned to the Placebo (PL) condition

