1061 considered as falling into three types: 1) missing completely at random, 2) missing at random, or 3)
1062 missing not at random. The type of missing data will dictate the approach. Assuming type 1, and that the
1063 number of missing values is low, we will use a standard listwise deletion procedure. However, assuming
1064 that a larger number of values is missing, and data are not missing completely at random, we will be able
1065 to apply missing data imputation methods.

1066 **Power Analysis:** A power analysis based on a proposed sample size of 90 subjects suggested that
1067 with an omnibus 2 between-groups (BL vs. PL) x 2 within-subjects (pre- vs post-treatment) mixed design,
1068 assuming a moderate effect size ($f = .25$), and $\alpha = .05$, there should provide be adequate power to detect
1069 most effects. First, the primary hypotheses of the study focus on interaction effects across groups (i.e.,
1070 treatment x session interactions), which will have exceptional power ($1-\beta = 0.99$) to detect a moderate
1071 effect size at $\alpha = .05$ (see Figure 18A). Paired comparisons within each group of will also have excellent
1072 power of .91 to detect moderate effect size changes ($d = .50$), with 2-tailed tests (see Figure 18B).
1073 Without regard to group differences, a sample size of 90 would yield power = 0.84 to detect a moderate
1074 linear association (i.e., $r \geq .30$) between a predictor variable (e.g., average sleep; change in sleep
1075 parameters, PTSD symptom severity; neurocognitive performance; etc.) and an outcome variable (e.g.,
1076 fMRI signal intensity changes; spectroscopic metabolite changes; etc.), with a two-tailed test at $\alpha = .05$
1077 (see Figure 16). Thus, the proposed sample size of $n = 45$ per group appears to provide adequate power
1078 for testing the major hypotheses of the proposed study.

FORM: Application for Human Research

| NUMBER | FORM DATE | PAGE |
|---------------|------------------|-------------|
| F200 | 02/2014 | 32 of 44 |

1079 **Functional Image Pre-Processing:** Functional neuroimaging data will be preprocessed in SPM8
1080 [123]. Following standard algorithms, functional images will be slice-time corrected, co-registered to
1081 their anatomical T1-weighted images, realigned, unwarped to correct for field inhomogeneity, normalized
1082 to the standard three-dimensional space of the Montreal Neurological Institute (MNI), spatially smoothed

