1310 For subjects who agree, their information will be saved for future use to allow possible contact for
1311 other studies conducted by the PI.

1312 A final study report will be made available to the sponsor, the Department of Defense (DoD). Only
1313 non-identifiable data will be shared. DoD maintains a secure file transfer system, "DoD SAFE," which
1314 can be used to securely transfer study information to the sponsor.

1315 Research data will be stored in a secure area for a period of 6 years following the conclusion of the
1316 study. All data and links will be destroyed as soon as possible.

1317 **11) Cost to subjects**

1318 There are no costs to subjects, except for their time.
1319

1320 **12) Subject compensation**

1321 Potential subjects who complete pre-screening surveys (*Recruitment Survey.pdf*) through
1322 crowdsourcing websites will be compensated in line with the specific site's payment policy (e.g., Amazon

FORM: Application for Human Research

| NUMBER | FORM DATE | PAGE |
|--------|-----------|----------|
| F200 | 02/2014 | 38 of 44 |

1323 Mechanical Turk will pay \$0.60 after the survey is completed, a rate of \$0.12 per min in compliance with
1324 research guidelines for fair wages within the MTurk community, with a predetermined 5-minute effort
1325 allotted).

1326 Subjects will receive \$1200 for completion of all three study sessions, successful adherence to
1327 daily light exposure treatment, and compliance with all study procedures and proper use of all study
1328 equipment. This payment is also intended to cover all transportation expenses to and from the study site.

1329 If subjects choose to withdraw from the study prematurely or are disqualified for any reason,
1330 subjects will be compensated according to the following schedule for the time subjects were undergoing
1331 scanning and testing:

- 1333 • Discontinuation during or following the initial intake visit: \$75 (\$25/hour, 3 hours max for day),
1334 following return and adherence of all study-related tasks and equipment.
- 1335 • Discontinuation before the end of second visit: \$17.05/hour, up to a maximum of 8.5 hours and
1336 \$145 for the day (i.e., max = \$220 total for both days), following return and adherence of all
1337 study-related tasks and equipment.
- 1338 • Discontinuation any time during the 6-week light exposure period: \$220 maximum total payment,
1339 following return and adherence to all study-related tasks and equipment.

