- 1340 • Fully compliant participants will receive \$980 for completion of all light exposure sessions, proper
1341 use of light meter, and completion of all research activities during the final visit. Payment to
1342 participants who discontinue their participation between the second visit and the final visit is
1343 variable depending on days of light exposure missed:

- 1344 ○ 1 day missed: Maximum total payment \$1200
- 1345 ○ 2 days missed: Maximum total payment of \$1195
- 1346 ○ 3 days missed: Maximum total payment of \$1190
- 1347 ○ 4 days missed: Maximum total payment of \$1180
- 1348 ○ 5 days missed: Maximum total payment of \$1160
- 1349 ○ 6 days missed: Maximum total payment of \$1120
- 1350 ○ 7 days missed: Maximum total payment of \$1040
- 1351 ○ 8 days missed: Maximum total payment of \$880
- 1352 ○ 9 days missed: Maximum total payment of \$560
- 1353 ○ More than 9 days missed: \$220 maximum from completion of first 2 visits

1354
1355 Payment cannot be rendered until all study-related equipment has been returned. In order to be
1356 compensated for participation in this study, subjects must be a U.S. citizen or other person legally entitled
1357 to earn money in the U.S. By law, payments to subjects may be considered taxable income.

1358
1359 **If the participant is an active duty military personnel**, the participant is not eligible to receive
1360 compensation for time spent completing assessments while they are "on duty". In accordance with Title
1361 24 United States Code 30, active duty military personnel must be on leave status during each of the three
1362 assessment sessions in order to be compensated. If the participant is on active duty, **it is their**
1363 **responsibility** to ensure that they have completed the appropriate paperwork for leave and obtained the

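### Section 15 lets staff withdraw randomised participants for non-compliance, and Visit 3 outcomes are then not sought, so the comparison may become a completer analysis shaped by adherence

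*Combined protocol and SAP*

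**What the plan says.** **Withdrawal (Section 15).** If it becomes evident that a "participant is unable or unwilling to comply with study procedures, research study staff may withdraw" that individual. The section adds that the Principal "Investigator reserves the right to remove any subject at his discretion from the study". After withdrawal, "information collected up to that point will be kept"; later outcome collection is not mentioned.

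**Payment (Section 12).** Full payment is $1200, of which $980 is for the light sessions and the final visit. One bullet, headed "Discontinuation any time during the 6-week light exposure period", caps payment at $220. The next bullet gives a sliding scale by light days missed, from $1200 for one day down to $560 for nine. Beyond nine days it is $220, described as the "maximum from completion of first 2 visits". That scale is introduced as payment to "participants who discontinue their participation between the second visit and the final visit is" variable.

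**Analysis (D. Data Analysis).** Behavioural outcomes become change metrics from baseline to post-treatment. Repeated-measures ANOVA and linear mixed models are named for the primary analyses of mood and sleep. If data are missing completely at random and the "number of missing values is low, we will use a standard listwise deletion procedure". With more missing values, not completely at random, imputation is allowed but no method is named. No intention-to-treat set, per-protocol set or estimand is defined.

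**Sample size (Section 7, General Procedure).** 108 are recruited "to reach a final n of 90 subjects, assuming 20% attrition".

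**The concern.** Adherence to the light is behaviour after randomisation. If it decides who stays in the study, the groups compared at Visit 3 need not be the groups that were randomised. Staff learn of non-adherence during treatment: under Compliance Monitoring, diary log-ins are tracked daily and participants are contacted after 48 hours of silence.

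Adherence could depend on arm. The devices differ in colour and output (1.23 against 0.35 mW/cm² and 214 against 188 lux, under At Home Six-Week Light Exposure Treatment), and Section 8 advises people with discomfort to stop using the device and contact the investigator. The text available does not say that those deciding on withdrawal are unaware of the arm.

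At stake is the blue-versus-amber contrast for outcomes measured only at Visits 2 and 3: clinician-rated PTSD severity, neurocognitive testing, sleep latency and imaging. An outcome not collected at Visit 3 cannot be obtained later. The follow-up survey does not fill the gap, because the Follow-Up paragraph offers it after participants complete the study.

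**Working it through.** **1. The plan's attrition figure.** 90 × (1 + 0.20) = 108, which reproduces the stated enrolment. Going from 108 to 90 is a loss of 18/108 = 16.7%, while a 20% loss from 108 would leave 108 × 0.80 = 86.4. I therefore use 16.7% to 20% as the plan's own scale of loss. (Dividing by 1 − 0.20 would give 113; that is a separate matter.)

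**2. The payment threshold.** Six weeks of daily use is 42 days. Missing 9 leaves 33/42 = 79% adherence, still partly paid. Missing 10 leaves 32/42 = 76%, paid $220. The sum forgone is 1200 − 220 = $980, or 980/1200 = 82% of the total.

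**3. The two payment bullets side by side.** Someone who stops in the light period after missing two days is capped at $220 by one bullet and at $1195 by the other. Both cannot apply. The scale makes sense if it is meant for people who reach Visit 3, since its top value is the full payment. On that reading, more than 9 missed days means nothing is paid for Visit 3.

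**4. Possible size of the bias.** The documents give no loss by arm and no link between adherence and outcome, so the following are assumptions: no true effect, completers only, 54 randomised per arm, and a correlation r of 0.2 to 0.5 between adherence and outcome. If the least adherent fraction d of an arm is lost, the mean of those remaining shifts by

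shift = r × φ(z_d) / (1 − d), with z_d = Φ⁻¹(d),

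and the bias b is the difference in shift between arms. The type I error is Φ(−1.96 − b/SE) + 1 − Φ(1.96 − b/SE), with SE = √(1/n₁ + 1/n₀) and n = 54(1 − d) in each arm.

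Example, 25% against 15%: φ(−0.674)/0.75 = 0.424 and φ(−1.036)/0.85 = 0.274. The difference is 0.149 before rounding of the two terms. Multiplying by 0.2 gives 0.030 SD and by 0.5 gives 0.075 SD.

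| Loss in the two arms | Bias (SD), r = 0.2 | r = 0.3 | r = 0.5 | Type I error |
|---|---|---|---|---|
| Equal (16.7% or 20%), same mechanism | 0 | 0 | 0 | 0.050 |
| 25% vs 15% | 0.030 | 0.045 | 0.075 | 0.052–0.064 |
| 30% vs 10% | 0.060 | 0.091 | 0.151 | 0.059–0.107 |
| 16.7% in both, outcome-related in one arm only | 0.060 | 0.090 | 0.150 | 0.059–0.110 |
| 20% in both, outcome-related in one arm only | 0.070 | 0.105 | 0.175 | 0.062–0.129 |

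The direction depends on which arm loses its poorer responders. Against the d = 0.50 that the plan calls moderate (stated for paired comparisons within a group), 0.030 to 0.175 SD is 6% to 35%.

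**5. Completers against all randomised.** If the 16.7% to 20% lost would have had no benefit and the others gain 0.50 SD, the effect over all randomised is 0.50 × 0.833 = 0.42 to 0.50 × 0.80 = 0.40 SD. The completer figure is then 1.20 to 1.25 times as large.

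**The case against.** A reader might infer four stronger things, none of which the documents support.

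- *That the trial becomes a complier analysis.* Withdrawal is permissive, the stated response to missed diary entries is contact rather than removal, and the wrist light data are evaluated only at the end of the study. On the coherent reading of the payment scale, people who miss 1 to 9 days stay and are paid $560 to $1200. No text restricts the analysis to compliers.
- *That non-adherers certainly go unpaid for Visit 3, or are barred from it.* The first depends on how the conflict in Section 12 is resolved. The second is stated nowhere.
- *That these losses will be listwise deleted.* That rule needs data that are few and missing completely at random. Loss driven by adherence falls under the imputation clause, and mixed models are also named.
- *That every efficacy contrast is biased.* Equal loss by the same mechanism gives no bias between arms. Arm-dependent adherence is a possibility, not a finding: the amber device is described as similar in appearance, and illuminance differs by 14% (214/188), though irradiance differs more.

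Some loss may also precede randomisation, which takes place at the end of Visit 2, and that loss cannot bias the comparison. The protocol reports more than 30 brain-injured participants completing these procedures with no discontinuation for burden. Actigraphy and diary data up to withdrawal would be kept.

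All of this stands, and it limits the claim. It does not answer it. Mixed models and imputation rest on what was observed, and for outcomes measured only at Visits 2 and 3 nothing is observed after baseline. They do not recover outcomes lost for reasons tied to the outcome itself. The pilot was in a different population, and the plan itself budgets for 20% attrition.

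**Conclusion.** The concern holds as a risk that the plan permits and does not address. Section 15 allows outcomes to be lost according to behaviour after randomisation. No text seeks Visit 3 from those affected, and no analysis set of all randomised participants is defined. The comparison may therefore become a completer analysis shaped by adherence.

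The size cannot be known from the documents. Under the assumed scenarios, bias between arms is about 0.03 to 0.18 SD, with type I error from 0.052 to 0.129; it is zero if loss is equal and by the same mechanism. These figures rest on the assumed loss rates, the correlation of 0.2 to 0.5 and a completers-only analysis. The type I error also rests on 54 randomised per arm, which takes all 108 recruited as randomised. The change is worth making because it is cheap and a missed Visit 3 cannot be recovered.

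**What to change.** 1. **Section 15:** after randomisation, limit removal from the study to participant request, safety or discovered ineligibility. State that missing or stopping light sessions does not by itself end participation, and that Visit 3 is sought from every randomised participant. This concerns data collection only; it does not touch the advice on when to stop using the device.
2. **D. Data Analysis:** make the primary analysis all randomised participants in the assigned arm, with an adherent-only analysis as secondary. Name the missing-data method and add a sensitivity analysis for data missing not at random.
3. **Section 12:** reconcile the two bullets, so that it is clear whether the missed-day scale covers people who attend Visit 3, people who discontinue, or both. Tying part of the final payment to Visit 3 attendance is an option, but it weakens the adherence incentive and the point does not depend on it.

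**Cost:** protocol wording, a few more Visit 3 sessions from non-adherers, and some dilution of the estimate. In the extreme case in step 5 of the working, 0.50 SD becomes 0.40 to 0.42 SD, which is the effect over everyone assigned to the light.
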